2.4. Visit Windows

As subjects do not always adhere to the protocol visit schedule, the following rules are applied to assign actual visits to protocol visits. Listed in [Table 2](#) are the visit windows and the target days for each visit. The reference day is Study Day 1 (which is the first day the study drug was taken in the double-blind phase).

If a subject has 2 or more actual visits in one visit window, the visit closest to the target day will be used as the protocol visit for that visit window. The other additional visit(s) will not be used in the summaries or analyses. If 2 actual visits are equidistant from the target day within a visit window, the later visit is used. If a visit window has no scheduled visits but does have unscheduled visits, then the unscheduled visit closest to the scheduled visit will be used.

All assignments will be made in chronological order. Once a visit is assigned to a visit window, it will no longer be used for a later time point except for the end point. Listed below ([Table 2](#)) are the visit windows and the target days (if applicable) for each visit defined in the protocol.

Table 2: Visit Windows

Parameter	Scheduled Visit Number	Time Interval (label on output)	Time Interval (Day) ¹	Target Time Point (Day)	Analysis Phase ⁵	
MINI Interview, Height, Serology	1	Screening	<1	-28 to -1	Screening	
LSAS, HDRS ₁₇	1	Screening	<1	-28 to -1	Screening	
	2	Baseline	≤1	1	DB Treatment	
	3	Week 1	2 to 10	7	DB Treatment	
	4	Week 2	11 to 21	14	DB Treatment	
	5	Week 4	22 to 42	28	DB Treatment	
	7	Week 8	43 to 70	56	DB Treatment	
SIGH-A	2	Baseline	≤1	1	DB Treatment	
	3	Week 1	2 to 10	7	DB Treatment	
	4	Week 2	11 to 21	14	DB Treatment	
	5	Week 4	22 to 42	28	DB Treatment	
	7	Week 8	43 to 70	56	DB Treatment	
	9	Week 12 End Point ²	71 to End of DB ⁴	84	DB Treatment	
CGI - I	3	Week 1	2 to 10	7	DB Treatment	
	4	Week 2	11 to 21	14	DB Treatment	
	5	Week 4	22 to 42	28	DB Treatment	
	7	Week 8	43 to 70	56	DB Treatment	
	9	Week 12 End Point ²	71 to End of DB ⁴	84	DB Treatment	
	SDS, GAD-7, SHAPS, MOS Sleep – R, Q-LES-Q	2	Baseline	≤1	1	DB Treatment
5		Week 4	2 to 42	28	DB Treatment	
7		Week 8	43 to 70	56	DB Treatment	
9		Week 12 End Point ²	71 to End of DB ⁴	84	DB Treatment	
Self-assessment of treatment experience	9	Week 12 End Point ²	2 to End of DB ⁴	84	DB Treatment	
12-Lead ECG, Body Weight	1	Screening	<1	-28 to -1	Screening	
	2	Baseline	≤1	1	DB Treatment	
	5	Week 4	2 to 56	28	DB Treatment	
	9	Week 12 End Point ²	57 to End of DB ⁴	84	DB Treatment	
	10	Follow Up ³	> End of DB ⁴	91 to 112	Post Treatment	
Vital Signs, Body temperature	1	Screening	<1	-28 to -1	Screening	
	2	Baseline	≤1	1	DB Treatment	
	3	Week 1	2 to 10	7	DB Treatment	
	4	Week 2	11 to 21	14	DB Treatment	
	5	Week 4	22 to 42	28	DB Treatment	
	7	Week 8	43 to 70	56	DB Treatment	
	9	Week 12 End Point ²	71 to End of DB ⁴	84	DB Treatment	
	10	Follow Up	> End of DB ⁴	91 to 112	Post Treatment	
	CSSR-S	1	Screening	<1	-28 to -1	Screening
		2	Baseline	≤1	1	DB Treatment
3		Week 1	2 to 10	7	DB Treatment	
4		Week 2	11 to 21	14	DB Treatment	
5		Week 4	22 to 35	28	DB Treatment	
6		Week 6	36 to 49	42	DB Treatment	
7		Week 8	50 to 63	56	DB Treatment	
8		Week 10	64 to 77	70	DB Treatment	

Table 2: Visit Windows

Parameter	Scheduled Visit Number	Time Interval (label on output)	Time Interval (Day) ¹	Target Time Point (Day)	Analysis Phase ⁵
	9	Week 12 End Point ²	78 to End of DB ⁴	84	DB Treatment DB Treatment
Clinical Laboratory Assessments	1	Screening	<1	-28 to -1	Screening
	2	Baseline	≤1	1	DB Treatment
	4	Week 2	2 to 21	14	DB Treatment
	5	Week 4	22 to 35	28	DB Treatment
	6	Week 6	36 to 49	42	DB Treatment
	7	Week 8	50 to 63	56	DB Treatment
	8	Week 10	64 to 77	70	DB Treatment
	9	Week 12 End Point ²	78 to End of DB ⁴	84	DB Treatment DB Treatment
	10	Follow Up ³	> End of DB ⁴	91 to 112	Post Treatment
Urine Drug Screen	1	Screening	<1	-28 to -1	Screening
	2	Baseline	≤1	1	DB Treatment
	5	Week 4	2 to 56	28	DB Treatment
	9	Week 12 End Point ²	57 to End of DB ⁴	84	DB Treatment DB Treatment
Alcohol Screen	1	Screening	<1	-28 to -1	Screening
	2	Baseline	≤1	1	DB Treatment
	4	Week 2	2 to 21	14	DB Treatment
	5	Week 4	22 to 42	28	DB Treatment
	7	Week 8	43 to 70	56	DB Treatment
	9	Week 12 End Point ²	71 to End of DB ⁴	84	DB Treatment DB Treatment
10	Follow Up ³	> End of DB ⁴	91 to 112	Post Treatment	
Pregnancy test	1	Screening	<1	-28 to -1	Screening
	2	Baseline	≤1	1	DB Treatment
	9	Week 12 End Point ²	2 to End of DB ⁴	84	DB Treatment DB Treatment
	10	Follow Up		91 to 112	Post Treatment
Physical Examination	1	Screening	<1	-28 to -1	Screening
	9	Week 12 End Point ²	2 to End of DB ⁴	84	DB Treatment DB Treatment
	10	Follow Up	> End of DB ⁴	91 to 112	Post Treatment

¹ Relative to first day of study medication

² End Point is defined as the last non-missing post-baseline measurement during the double-blind treatment phase.

³ Only in case of any clinical significant abnormality observed at Week 12 (except for weight)

⁴ End of DB = the end of the double-blind treatment phase

⁵ On output tables, DB Treatment will be presented as “Double-Blind Treatment”.

2.5. Analysis Sets

2.5.1. All Subjects Analysis Set

The All Subjects analysis set includes all subjects with information entered into the clinical database. This set will be used for the listings unless specified otherwise.

2.5.2. All Randomized Analysis Set

The All Randomized analysis set includes all subjects who were randomized (i.e., subjects who reported a randomization date, or were assigned a randomization number) regardless of whether or not the treatment was received.

This analysis set will be used for summarizing the overall study completion/withdrawal information.

2.5.3. Intent-to-Treat (ITT) Analysis Set

The ITT analysis set is defined as all randomized subjects who received at least one dose of study medication (either placebo or JNJ-42165279), and have at least one assessment in the double-blind treatment phase on any of the efficacy parameters. Subjects who withdrew early from the study at the time of study suspension will not be included in the ITT analysis set (7 placebo subjects, 8 JNJ-42165279 subjects). Subjects who had already completed the study at the time it was suspended, however, will be included in the ITT set (9 placebo subjects, 9 JNJ-42165279 subjects).

The ITT analysis set is the analysis set for the efficacy analyses.

2.5.4. Safety Analysis Set

The Safety analysis set is defined as all randomized subjects who received at least one dose of study medication (either placebo or JNJ-42165279). Screen failures and randomized subjects who received no double-blind study medication will be excluded from the Safety analysis set.

The Safety analysis set is the analysis set for the safety analyses.

2.5.5. Per Protocol Analysis Set

The Per Protocol analysis set includes all ITT subjects who did not have a major protocol deviation during the study. In case there is a substantial amount of subjects with a major protocol deviation, a sensitivity analysis of the primary efficacy parameter will be performed for the per protocol analysis set.

2.6. Definition of Subgroups

Some of the secondary efficacy endpoints will be analyzed for the subgroup of subjects with comorbid MDD/GAD. See Section 5.4 for a definition of these exploratory endpoints.

Exploratory analyses of selected parameters will be performed for the subgroup of subjects who enrolled prior to study suspension versus those who enrolled after the study had resumed.

Exploratory sensitivity analyses of the primary efficacy parameter will be performed for the subgroup of subjects who did not meet criteria for sufficient compliance based on pharmacokinetic results. These criteria are defined by the clinical pharmacology department.

3. INTERIM ANALYSIS AND DATA MONITORING COMMITTEE REVIEW

A blinded interim analysis for the purpose of sample size re-estimation may be performed after 50% of the subjects are recruited if the observed standard deviation substantially deviates from the hypothesized standard deviation, or if the drop-out rate substantially deviates from the assumed drop-out rate.

No interim analysis for efficacy is planned.

4. SUBJECT INFORMATION

Subject information will be summarized for the Safety Analysis Set and listings will be created for the All Randomized analysis set.

4.1. Demographics and Baseline Characteristics

The following demographic and baseline characteristics will be listed and summarized by treatment group and overall:

Age (years), sex, race, ethnicity, weight (kg), height (cm), body mass index (BMI, calculated as weight (kg)/[height(m)]²), country, presence of comorbid major depressive disorder (MDD), presence of comorbid generalized anxiety disorder (GAD).

Continuous variables (age, weight, height and BMI) will be summarized using descriptive statistics (N, mean, standard deviation [SD], median and range [minimum and maximum]). Categorical variables (race, ethnicity, country, presence of comorbid MDD, presence of comorbid GAD) will be summarized using a frequency distribution with the number and percentage of subjects in each category.

Psychiatric history at baseline will be summarized by treatment group and overall using descriptive statistics for the following assessments: LSAS total score, SIGH-A total score, HAM-A₆ score, HDRS₁₇ total score, HDRS₁₇ anxiety/somatization factor score, HAM-D₆ score.

The summary of demographics and baseline characteristics and psychiatric history at baseline will be created for both the Safety Analysis Set and the ITT Analysis Set. The summary will also be presented by country and by enrollment prior to/after study suspension.

Listings will be created for the following assessments:

Randomization information, inclusion/exclusion criteria, childbearing potential, date of last menses, date of signature on informed consent, issue date of the protocol the subject consented to at study enrollment, preplanned surgery/procedures, psychiatric evaluation (M.I.N.I.), medical history, comments, study execution period.

4.2. Disposition Information

The number and percentage of subjects in the All Randomized Subjects, ITT, Per Protocol and Safety analysis sets will be presented overall, and by country and center. In addition, summaries of the reasons for exclusion from each analysis set (i.e., Per Protocol set and ITT set) will be provided. The number of screen failures together with the withdrawal reason will be presented.

The distribution of the number of subjects who complete the entire course of treatment and who discontinue will be presented by treatment group and overall. The distribution of study

termination reasons will also be presented. In addition, the number and percentage of subjects who discontinue on or prior to each study visit will be summarized by treatment group and overall. The distribution of time to discontinuation will be presented graphically using Kaplan-Meier estimates. The time to treatment discontinuation will be calculated as the duration (in days) from Study Day 1 (defined in Section 2.3.1) to treatment discontinuation. Subjects who complete the double-blind treatment period will be censored at the end of treatment date.

Study completion and withdrawal information for each subject will also be presented in a listing.

4.3. Treatment Compliance

The number of tablets dispensed and returned at each visit will be listed.

4.4. Extent of Exposure

Study drug administration information will be presented for each subject in a data listing.

Treatment duration is defined as the number of days between the first and the last day of study drug in the double-blind treatment phase: last day of study drug administration – first day of study drug administration + 1.

Treatment duration will be listed and summarized by treatment group using descriptive statistics (N, mean, SD, median, and range). A frequency distribution will also be provided using the following categories: <1 week (<7 days), 1-<2 weeks (7-<14 days), 2-<4 weeks (14-<28 days), 4-<6 weeks (28-<42 days), 6-<8 weeks (42-<56 days), 8-<10 weeks (56-<70 days), 10-<12 weeks (70-<84 days) and ≥ 12 weeks (≥ 84 days).

4.5. Protocol Deviations

Deviations that occurred during the study will be listed by treatment group. Major deviations will be presented as grouped by the Data Management Group prior to the unblinding.

4.6. Prior and Concomitant Medications

The following groups of medication will be tabulated by treatment group, by medication class and generic term of the medication:

- Prior medications: medications with start date/time and end date/time prior to first dose intake
- Prior and ongoing medications: medications with start date/time prior to first dose intake and end date/time after first dose intake
- Concomitant medications: medications with start date/time after first dose intake

Data listings will be provided for all medications received from the signing of informed consent prior to study start and concomitantly during the study.

5. EFFICACY

All efficacy analyses will be based on the ITT analysis set. The efficacy variables in this study are listed in [Table 3](#).

All efficacy data will be listed for the subjects in the ITT analysis set.

Table 3: Efficacy Variables

Endpoint	Scale*
Primary	LSAS total score
	LSAS fear/anxiety subscale
	LSAS avoidance subscale
	LSAS $\geq 50\%$ improvement from baseline on total score
	LSAS $\geq 30\%$ improvement from baseline on total score
Secondary	SIGH-A total score
	HAM-A ₆ score
	HDRS ₁₇ total score
	HDRS ₁₇ anxiety/somatization factor score
	HAM-D ₆ score
	CGI-I
	SIGH-A $\geq 50\%$ improvement from baseline on total score
	SDS
Exploratory	GAD-7
	SHAPS
	MOS Sleep - R
	Q-LES-Q
	Self-Assessment of Treatment Experience
	HDRS ₁₇ total score in subjects with comorbid MDD
	HDRS ₁₇ anxiety/somatization factor score in subjects with comorbid MDD
	HAM-D ₆ score in subjects with comorbid MDD
	SIGH-A total score in subjects with comorbid GAD
	HAM-A ₆ score in subjects with comorbid GAD
	HDRS ₁₇ $\geq 50\%$ improvement from baseline on total score in subjects with comorbid MDD
	HDRS ₁₇ $\geq 30\%$ improvement from baseline on total score in subjects with comorbid MDD
	SIGH-A $\geq 50\%$ improvement from baseline on total score in subjects with comorbid GAD

* CGI-I = Clinical Global Impression – Improvement; GAD-7 = Generalized Anxiety Disorders; HAM-A₆ = Hamilton Anxiety Rating Scale; HAM-D₆ = Hamilton Depression Rating Scale; HDRS₁₇ = Hamilton Depression Rating Scale; LSAS = Liebowitz Social Anxiety Scale; MOS Sleep – R: Medical Outcomes Study Sleep-Revised; SDS = Sheehan Disability Scale; Q-LES-Q = Quality of Life Enjoyment and Satisfaction Questionnaire; SHAPS = Snaith-Hamilton Pleasure Scale; SIGH-A = Structured Interview Guide for the Hamilton Anxiety Scale

5.1. Analysis Specifications

5.1.1. Level of Significance

The overall Type I error rate for testing the JNJ-42165279 group versus the placebo group for the primary efficacy analysis will be controlled at the 1-sided significance level of 0.20.

5.1.2. Imputation Methods for Missing Items

Imputation of missing individual items will apply only to the LSAS, as described in Section 5.2.1. For all other scales where multiple items are summed to create a total score, if any item of the scale is missing on a visit, the total score for that scale at that visit will be left blank.

5.2. Primary Efficacy Endpoint – LSAS Total Score

5.2.1. Definition

The primary efficacy endpoint will be the improvement in social anxiety symptoms, as measured by the change from baseline in the LSAS total score from baseline to the 12-week endpoint in the double-blind treatment phase.

The LSAS was designed to assess the range of social interaction and performance situations that individuals with social phobia may fear and/or avoid (Liebowitz, 1987)⁶. The 24 items in the scale are divided into two subscales that address social interactional (11 items) and performance (13 items) situations. The clinician asks the patient to rate fear and avoidance during the past week on 0–3 Likert-type scales; however, the clinician is given latitude to question the patient’s responses and adjust the ratings accordingly. An example of the LSAS is provided in the [Attachment](#).

An overall total score is calculated by summing the 24 fear and 24 avoidance scores. The LSAS total score has a maximum of 144, with higher scores indicating higher probability of social anxiety disorder.

If an LSAS item is missing, it will be imputed with the closest integer to the average of the remaining items within the LSAS subscale (fear/anxiety, avoidance) at that time point and then the total will be summed. If more than 1 item is missing, no imputation will be performed and the total LSAS score will be left missing. Imputation of item scores is performed prior to determining the endpoint for the LSAS.

5.2.2. Analysis Methods

5.2.2.1. Primary Analysis

Descriptive statistics of actual values and changes from baseline for the LSAS total score at each scheduled time point and endpoint will be provided by treatment group (mean, SD, median and range). A mean-SE plot over time will be presented for the LSAS total score observed values by treatment group. Listings will be created with LSAS item scores and the LSAS total score.

The JNJ-42165279 treatment group will be compared to placebo by means of a mixed-effects model using repeated measures (MMRM) with time, treatment (placebo, JNJ-42165279) and time-by-treatment interaction as factors, baseline LSAS total score and age as a continuous covariate and country and presence of comorbid MDD as categorical covariates. An unstructured variance-covariance matrix will be used. In case of convergence problems, simpler variance-covariance structures such as Toeplitz or AR(1) will be considered. The selection of any of these structures will be determined after exploration of the observed

correlation structure. The treatment-placebo differences will be obtained using the appropriate contrast in the MMRM model at the 12-week endpoint.

A one-sided p-value with level of significance of 20% will be derived from the SAS results based on the above mixed-effects model (two-sided p-values at 40% significance level). The reduction in LSAS total score is expected to be larger after dosing with JNJ, so the one-sided p-value will be calculated as described in [Table 4](#).

Table 4: Calculation of one-sided p-value

Parameter	H_a	Estimated difference Mean _{JNJ} – Mean _{Pla}	One-sided p-value
Change in LSAS total score at Week 12	Mean Chg _{JNJ} - Mean Chg _{Pla} < 0 (larger reduction expected in JNJ vs pla)	< 0	p-value _(2-sided test) / 2
		> 0	1 – (p-value _(2-sided test) / 2)

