### 4.1. Inclusion Criteriaa

Each potential subject must satisfy all of the following criteria to be enrolled in the study unless otherwise specified:

- 1. Subject must be a man or woman between 18 and 64 years of age, inclusive.
- 2. Subjects must have a primary DSM-5 diagnosis of SAD except those with performance only as a specifier. Subjects with a diagnosis of comorbid Generalized Anxiety Disorder (GAD) or Major Depressive Disorder (MDD) may be included if the investigator considers SAD to be the predominant diagnosis. Subjects with current or lifetime history of ADHD and specific phobia may be included as well.
- 3. Subjects must have a Liebowitz Social Anxiety Scale score  $\geq$  70 at screening and baseline.
- 4. Subjects with a current episode of MDD must have a HDRS17 total score  $\leq 18$
- 5. Subjects must have a body mass index (BMI=weight/height) between 18 and 35 kg/m^2, inclusive, at screening.
- 6. Criterion modified by Amendment 3.
  - 6.1. Before randomization, a **woman** must be either:
  - Not of childbearing potential: postmenopausal (>45 years of age with amenorrhea for at least 12 months, or any age with amenorrhea for at least 6 months and a serum follicle stimulating hormone (FSH) level >40 IU/L); permanently sterilized (e.g., tubal occlusion, hysterectomy, bilateral salpingectomy); or otherwise be incapable of pregnancy
  - Of childbearing potential and practicing a highly effective method of birth control consistent with local regulations regarding the use of birth control methods for subjects participating in clinical studies (i.e. one that results in a less than 1% per year failure rate when used consistently and correctly). This may include:
    - Established and ongoing use of oral hormonal methods of contraception in combination with barrier methods.
    - Established and ongoing use of patch, injected or implanted hormonal methods of contraception.
    - Placement of an IUD or IUS.

Accepted barrier methods as indicated above include:

<sup>a This section has been amended per Amendments INT-1 and 3.

- condom with spermicidal foam/gel/film/cream/suppository
- occlusive cap (diaphragm or cervical/vault caps) with spermicidal foam/gel/film/cream/suppository

Note that a barrier method on its own is not sufficient.

- Male partner sterilization (the vasectomized partner should be the sole partner for that subject).

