1.2. Trial Design

This is a multi-center, double-blind, placebo-controlled, randomized, parallel-group study assessing the efficacy, safety, and tolerability of JNJ-42165279 during 12 weeks of treatment in subjects with SAD.

Approximately one-hundred twenty-two (122) subjects will be enrolled in this 12 week treatment study randomly assigned in a 1:1 ratio to either 25 mg of JNJ-42165279 or placebo (dosed once daily orally).

For all enrolled subjects, this study will consist of a 28-day eligibility screening period, a 12 week double-blind treatment period and a follow-up examination between 7 and 28 days after last dose. The study duration for each subject will be maximally 20 weeks.

The study will be an outpatient study.

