1.4. Sample Size Justification

The sample size for the study is based on the assumption of a treatment difference of at least 10 points in the mean change from baseline to the endpoint in LSAS total score between JNJ-42165279 treatment group and placebo. A standard deviation of 24 in the change in LSAS total score from baseline is used based on published data.^{7,10,11} To detect the treatment difference of 10 points (which is judged to be clinically relevant^{7,10,11}) with a power of 90% at an overall 1-sided significance level of 0.20, 53 subjects in each group are required. When adjusted for a drop-out rate of approximately 15% of subjects, the required number of subjects is 61 per treatment group.

The impact of this sample size (N=122) on the JNJ- 42165279 effect size to be detected for the other continuous secondary and exploratory endpoints for different values of significance level and power, assuming a drop-out rate of 15%, are presented in [Table 1](#).

Table 1: JNJ-42165279 effect size to be detected for different values of significance level and power, assuming a drop-out rate of 15%

I-sided significance level	Power	Effect size to be detected
0.10	80%	0.4
0.10	90%	0.5
0.20	80%	0.3
0.20	90%	0.4

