2.3.3. Baseline

Baseline is defined as the last non-missing observation prior to first dose of study drug.

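### The primary model's only LSAS covariate is the last pre-dose score; adding the screening LSAS total is a cheap change with a small and uncertain gain in precision

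*SAP*

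**What the plan says.** - **Two pre-dose ratings.** The protocol's Time and Events Schedule marks the LSAS at Visit 1 (screening) and Visit 2 (Day 1). Protocol 9.1.2 and 9.1.3 list it among the screening and Day 1 pre-dose procedures.
- **Entry rule.** Protocol 4.1, criterion 3: "Subjects must have a Liebowitz Social Anxiety Scale score" of 70 or more at both screening and baseline.
- **One of them is used.** SAP 2.3.3: "Baseline is defined as the last non-missing observation prior to first dose of study drug". SAP 5.2.2.1 then adjusts for "baseline LSAS total score and age as a continuous covariate and country and presence of comorbid MDD as categorical covariates".
- **Other models.** The ANCOVAs in SAP 5.2.2.2 carry the same covariates. The secondary MMRM in that section adds race, history of MDD and baseline SDS. None includes the screening LSAS.
- **Room to add it.** Protocol 11.3 permits further covariates of interest in the MMRM. The SAP has already used that freedom: age is in its primary model but not in the protocol's list.

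**The concern.** The LSAS is a clinician rating, and SAP 5.2.1 lets the rater question and adjust the subject's answers, so some rating error is to be expected. Requiring 70 or more narrows the spread of true severity among those enrolled without reducing that error. A single pre-dose score is then a noisier marker of severity than it would be in an unselected sample, and adjusting for it removes less of the Week 12 variance than adjusting for severity itself would.

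A second reading of the same construct, taken before randomisation and already in the database, can recover part of that loss without bias. What is at stake is the width of the interval for the primary contrast and a little power.

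**Working it through.** **Step 1. Reproduce the planned sample size.** SAP 1.4 gives the inputs: "assumption of a treatment difference of at least 10 points"; "A standard deviation of 24 in the change in LSAS total score from baseline is used"; and "with a power of 90% at an overall 1-sided significance level of 0.20, 53 subjects in each group are required". Allocation is 1:1 (SAP 1.2).

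n per arm = 2 × (z₀.₈₀ + z₀.₉₀)² × SD² / Δ² = 2 × (0.8416 + 1.2816)² × 24² / 10² = 51.9, so 52 by the normal approximation. With the noncentral t, power is 0.8996 at 52 and 0.9031 at 53, which gives the stated 53.

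Reference precision at 53 per arm: SE = 24 × √(2/53) = 4.66. Power = Φ(10/4.66 − 0.8416) = 90.4% (normal approximation).

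**Step 2. Gain from a second pre-dose score.** Let r1 be the correlation of Day 1 with Week 12, r2 that of screening with Week 12, and r12 that of screening with Day 1. With Day 1 in the model, the residual variance is the same whether the outcome is the Week 12 score or the change from Day 1. Then:

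- R² with both scores = (r1² + r2² − 2·r1·r2·r12) / (1 − r12²)
- variance ratio = (1 − R²) / (1 − r1²)

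None of the three correlations is in the documents, so a range is shown. SD 24 is treated as the residual SD already reached with Day 1 adjustment, which is also an assumption. The net column multiplies by 1.01 for one degree of freedom out of roughly 100.

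| r1 | r12 | r2 | Ratio, gross | Ratio, net | Power at 53 per arm, gross |
|---|---|---|---|---|---|
| 0.4 | 0.6 | 0.40 | 0.952 | 0.962 | 91.2% |
| 0.4 | 0.6 | 0.36 | 0.973 | 0.983 | 90.9% |
| 0.4 | 0.7 | 0.40 | 0.966 | 0.976 | 91.0% |
| 0.4 | 0.8 | 0.36 | 0.995 | 1.005 | 90.5% |
| 0.5 | 0.7 | 0.50 | 0.941 | 0.951 | 91.5% |
| 0.5 | 0.8 | 0.50 | 0.963 | 0.973 | 91.1% |
| 0.5 | 0.8 | 0.45 | 0.991 | 1.001 | 90.5% |
| 0.5 | 0.8 | 0.40 (= r1·r12) | 1.000 | 1.010 | 90.4% |

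Worked example, fifth row: R² = (0.25 + 0.25 − 0.35) / 0.51 = 0.294, and the ratio is 0.706 / 0.75 = 0.941.

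More favourable corners exist. With r1 = r2 = 0.7 and r12 = 0.6 the gross cut is 24%. That would need Day 1 to predict a rating 12 weeks later better than it matches one taken at most 28 days earlier, so I give it no weight.

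**Step 3. Check with the entry rule built in.** Simulations truncated both pre-dose scores at 70. Their inputs are assumptions as well.

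- *No change in true severity between the two visits.* With true severity mean 80-90 and SD 15-18, rating error SD 7-12 and change SD 23-24, the gross cut was 1.7-6.0%.
- *0-8 points of true drift between visits.* With rating error SD 4-12 and change SD 22.4-24.7, the gross cut was 0.2-3.7%.
- *The planned type of MMRM, one common covariate slope across visits, 0-8 points of drift.* The gross cut was about 0.4-6%, mostly 1-4%. It agreed with the single-visit calculation to within 0.1 percentage point.

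**Step 4. Translate to power at 53 per arm, net of the degree of freedom.**

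- No gain: ratio 1.01, SE 4.69, power 90.2%.
- Net gain 3%: SE = 4.66 × √0.97 = 4.59, power 90.9%. This is equivalent to 0.03 × 53 ≈ 1.6 completers per arm.
- Gross 6%: net ratio 0.94 × 1.01 = 0.949, SE 4.54, power 91.3%.

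**The case against.** The strongest reply is that nothing here is wrong. The MMRM is prespecified, agrees with the protocol, adjusts for baseline LSAS, age and both stratification factors, and reaches 90% power as designed. Covariate choice was considered, and this is one more candidate. All of that stands.

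Three stronger readings are tempting, and the documents do not support them:

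- **That the model adjusts for nothing but the Day 1 LSAS.** This is true only among LSAS measures. Age, country and comorbid MDD are also in the model.
- **That the precision is free, with an assured gain of several percent.** The extra term costs about 1% of variance. If screening predicts Week 12 only through Day 1, the gain is zero and the net effect is slightly negative. Screening can be up to 28 days before Day 1, so true severity may move between the ratings, which weakens the older one.
- **That no randomised subject can lack either score.** Criterion 3 makes a missing score rare but not impossible. SAP 5.2.1 leaves the total missing when more than one item is missing. If Day 1 is missing, SAP 2.3.3 already falls back to screening, and the two covariates coincide.

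Two further objections carry less weight. The common slope across visits in the MMRM made no material difference in the simulation. The missing-score problem needs one sentence in the SAP.

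**Conclusion.** The point holds as a small efficiency improvement to a valid plan. It reveals no bias, no contradiction and no shortfall in power. A second pre-randomisation measure of the primary outcome is collected from essentially every randomised subject and left out of every planned model.

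The likely net gain is 0-3% of the Week 12 residual variance. Even the top of the plausible gross range adds only about 0.9 percentage points of power (90.4% to 91.3%). These figures rest on assumed correlations, rating error and drift, and on reading SD 24 as the residual SD after Day 1 adjustment. The documents fix only the entry threshold, the visit schedule and the planning values in SAP 1.4. I am confident of the direction unless screening adds nothing beyond Day 1; the size is uncertain.

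**What to change.** Before unblinding:

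1. In SAP 5.2.2.1, and in both ANCOVAs of 5.2.2.2, add the screening LSAS total as a second continuous covariate beside the existing baseline. Leave the definition of change (from Day 1) and the Week 12 contrast as they are.
2. Add one line for a missing Day 1 or screening total, for example using the available score for both covariates so that no subject is dropped.

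The cost is one degree of freedom and two or three lines of SAP text, with no new data. The SAP introduction states that no efficacy data were analysed at the suspension and that the efficacy datasets of subjects unblinded then stay secured until final database lock. The covariate can therefore still be fixed without knowledge of efficacy results. HDRS17 is also rated at both visits and could be treated the same way; that is optional, and its gain has not been quantified.
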